8.2.2 Supplementary Table Shells

Table 8: Longitudinal Patterns of P2Y₁₂ use

	Overall (N=patients)	Copayment Intervention (N=patients)	Usual Care (N=patients)
Overall Duration of any P2Y ₁₂			
Duration of initial P2Y ₁₂			
Summed duration of initial P2Y ₁₂			

Statistical Analysis Plan

Table 9a: Kaplan-Meier Cumulative Incidence

Outcome Time (days)*	Overall (N=X patients)			Copayment Intervention (N=X patients)			Usual Care (N=X patients)		
	KM rate (95% CI)	N remaining	N events	KM rate (95% CI)	N remaining	N events	KM rate (95% CI)	N remaining	N events
MACE 30 180 365									
All-cause death 30 180 365									
MI 30 180 365									
Stroke 30 180 365									
BARC 2+ bleed 30 180 365									
BARC 3+ bleed 30 180 365									
GUSTO Moderate/Severe Bleed 30 180 365									
Unplanned Revascularization 30 180 365									
Cardiovascular death 30									

Statistical Analysis Plan

180									
365									
MACE+Unplanned Revascularization									
30									
180									
365									

*Time (days) from discharge

Statistical Analysis Plan

Table 9b: Kaplan-Meier Cumulative Incidence of MACE among Subgroups

Subgroup Time (days)*	Overall (N=X patients)	Copayment Intervention (N=X patients)			Usual Care (N=X patients)		
	N events	KM rate (95% CI)	N remaining	N events	KM rate (95% CI)	N remaining	N events
Age ≥ 65: 30 180 365							
Age < 65: 30 180 365							
Male: 30 180 365							
Female: 30 180 365							
Private Insurance: 30 180 365							
Government Insurance: 30 180 365							
White: 30 180 365							
Non-white: 30							

Statistical Analysis Plan

180 365							
STEMI: 30 180 365							
NSTEMI: 30 180 365							
In-hosp PCI: 30 180 365							
No In-hosp PCI: 30 180 365							

*Time (days) from discharge

Statistical Analysis Plan

8.3 Appendix: List of Adjustment Variables

8.3.1 Adjustment Variables for Primary Models

Variable	Variable Type
Intervention	Yes/no
Randomization scheme	Categorical (2:1 vs. 1:1 scheme)
Interaction* between intervention and randomization scheme	Categorical
Site MI volume	Categorical (high vs. low)
Site % Ticagrelor use	Categorical (high vs. low)
Age	Continuous
Male gender	Yes/no
Race	Categorical (white vs. nonwhite)
Insurance Payors	Categorical (private vs. non-private)
Region	Categorical (Northeast, West, South, vs. Midwest)
Propensity for intervention	Continuous

*We will test for significant interaction and will drop if the interaction term is not significant.

Statistical Analysis Plan

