1.4 Sample Size Justification

The proposed sample size has been determined to provide adequate statistical power for the co-primary study objectives related to the copayment reduction intervention. The co-primary objective determines whether patient copayment reduction leads to greater persistence to P2Y₁₂ receptor inhibitor therapy at one year after hospital discharge. The hypothesis underlying this objective is that reducing patient copayment in a contemporary population of AMI patients will result in a significant increase in persistence to P2Y₁₂ receptor inhibitor therapy at one year, when compared with usual care. An increase of 4% in the persistence to P2Y₁₂ receptor inhibitor therapy would be considered a clinically important difference[1]. To achieve this objective with a patient-level randomization design, a sample size of 5392 patients would provide greater than 90% power with a two-sided Type I error rate of 0.05. A sample size of 4622 patients would provide greater than 85% power under the same assumptions. These power calculations are based on the assumption that the expected one-year persistence rate in the control group is 70%[1]. These calculations are based on the two group continuity corrected chi-square test statistic and assume that all observations are independently distributed. However, the sample size needs to be adjusted due to the cluster randomized design. We have applied the method described by Eldridge et al. [2] which accounts for the coefficient of variation (CV) of cluster

Statistical Analysis Plan

size and the intra-cluster correlation (ICC). Based on prior multicenter studies, we anticipate an ICC for this endpoint of approximately 0.025. Assuming a total of 300 sites randomized (1:1) with an average sample size of 36.67 patients per site and a CV of 0.65 would yield a design effect of approximately 2.28. The CV of 0.65 has been suggested by others and can be guided by providing minimum and maximum enrollment at the site level [2]. Therefore, a total sample size of 11,000 patients enrolled at 300 sites would result in an effective sample size of 4827 and be sufficient to provide between 85% and 90% power to detect an absolute 4% difference between treatment groups in the cluster randomized design.

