Patient-reported persistence to antiplatelet therapy will be validated using pharmacy records that will be collected on a subset of the overall study population. The assumed standard deviation of 0.25 (for the proportion of days covered) is based on a recent randomized clinical trial to assess an intervention designed to improve adherence [4]. Assuming 1:1 randomization and a two-sided Type I error rate of 0.05, a sample size calculation based on the two-sample t-test suggests that a total sample size of 1644 patients will yield 90% and a total sample size of 2034 will yield 95% power. A random sample of 2400 patients from the 300 sites randomized with a CV of 0.25 and an ICC of 0.025 would yield a design effect of approximately 1.26. The resulting effective sample size of 2021 patients would yield approximately 95% power to detect a difference of 4% between the patient copayment reduction intervention and control groups. The target sample size of 2500 patients with pharmacy records allows for 4% missing data due to records that are not available.

2. General Considerations for Data Analysis

We will include a detailed flow diagram showing the number of participants' eligible, number of subjects randomized to Copayment Intervention and Usual Care arms, numbers of subjects lost to follow-up or excluded from analyses, and the number of subjects analyzed for the key study endpoints. Additionally, we will describe the number of clinical sites in Copayment Intervention and Usual Care arms including the mean (median, range) for key study elements by site. Key elements will include the following items: descriptions of participants, interventions, objectives, outcomes, and sample size justification; and details about the randomization procedure, factors used to stratify randomization, (lack of) blinding, statistical methods, participant flow, dates of recruitment, baseline data by individuals and by cluster, numbers analyzed, outcomes and estimation, adverse events, and a discussion. These elements are based on the CONSORT statement for cluster randomized studies [5].

After Steering Committee consensus, the randomization scheme was changed from 1:1 to 2:1 Usual Care vs. Intervention effective November 16, 2015. Randomization schema was added below as a covariate for adjustment.

All analyses will be conducted using SAS version 9.4 or higher software. All tests will be two-sided and a p-value of <0.05 will be considered statistically significant.

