3.1 Non-persistence with antiplatelet therapy at 1 year

The co-primary endpoint of long-term non-persistence will be assessed using patient-reported medication non-persistence. Permanent and temporary discontinuation of a P2Y₁₂ receptor inhibitor will be queried at each follow-up interview. For patients with missing patient-reported medication information, pharmacy fill data will be used to ascertain persistence. Patients who have continued P2Y₁₂ receptor inhibitor use at one year from discharge with less than 30

Statistical Analysis Plan

continuous days of interruption will be considered persistent. We will use the last observation carried forward (LOCF) method for patients who died before one year or had missing 1 year P2Y₁₂ status.

The co-primary objective determines whether patient copayment reduction leads to higher long-term persistence with antiplatelet therapy at one year. The study endpoint for this objective is the proportion of patients at one year who had an interruption ≥ 30 days of P2Y₁₂ receptor inhibitor. The primary analysis will be a logistic regression model with parameters estimated using generalized estimating equations (GEE) to account for within hospital clustering and adjustment for selected patient characteristics (Section 8.3.1) which includes a propensity score for intervention (Section 8.3.2). The propensity score will be estimated using a logistic regression model for intervention group. Categorical variables will be included as sets of indicator variables. Continuous variables will be included assuming a simple linear relationship. Balance of covariates between intervention and usual care arms will be assessed using standardized differences as recommended by Austin [6]. We will assess functional form and possible transformations of the propensity score to be included in the outcome model. Cluster heterogeneity will be quantified using ICCs calculated from unadjusted and adjusted models. We will calculate the ICCs across all hospitals and also by treatment group.

After Steering Committee consensus, the randomization scheme was changed from 1:1 to 2:1 Usual Care vs. Intervention effective November 16, 2015. Randomization schema was added as a covariate for adjustment as shown in Section 8.3.1 and to the propensity model as shown in Section 8.3.2.

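### A significance test decides whether both co-primary models keep an intervention-by-scheme interaction, and the SAP names no primary contrast if it is kept

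*SAP*

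**What the plan says.** The adjustment list in SAP section 8.3.1 includes intervention, randomization scheme and "Interaction* between intervention and randomization scheme". The footnote to the third term reads "We will test for significant interaction and will drop if the interaction term is not significant". Sections 3.1 (GEE logistic model for non-persistence) and 3.2 (Cox model for MACE) both take their adjustment variables from this list, so the rule governs both co-primary analyses.

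The body text describes something simpler: "Randomization schema was added as a covariate for adjustment as shown in Section 8.3.1". It mentions neither an interaction nor a step that tests and drops it.

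The footnote gives no significance level. The only threshold is the general one in section 2: "All tests will be two-sided and a p-value of <0.05 will be considered statistically significant". The shells for Tables 3a and 4a provide one adjusted hazard ratio or odds ratio per outcome.

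**The concern.** The outcome data decide what the intervention coefficient means. Without the interaction it is a common effect adjusted for scheme. With it, the same row of output is the effect among sites randomized under the reference scheme. In that branch the SAP does not say which scheme is the reference, whether an average over schemes is formed, or how success is judged. The objectives in section 1.1 are trial-wide, so a one-scheme effect does not answer them.

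The interaction is tested separately for each endpoint, so the two co-primary results could come from models of different form. The rule also reaches analyses that reuse the primary adjustment, such as sections 4.1 to 4.3, the subgroup models and the random-intercept models of section 6.

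Prespecifying the rule does not remove the problem. The interaction statistic is correlated with each scheme-specific effect. A chance interaction under the null therefore tends to come with a spuriously large effect in one scheme, and the stated 5% error rate is at risk.

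**Working it through.** **1. The plan's own figures.** Section 1.4 states that "a sample size of 5392 patients would provide greater than 90% power with a two-sided Type I error rate of 0.05". Take 70% against 74% and, per arm, n = [1.96·√(2p̄q̄) + z_power·√(p₁q₁ + p₂q₂)]² / 0.04². At 90% power this gives 2646 per arm. The continuity correction (n/4)·[1 + √(1 + 4/(0.04n))]² raises it to 2696, or 5392 in total, as stated. The same steps give 4622 for 85% power. The design effect is 1 + [(0.65² + 1)·36.67 − 1]·0.025 = 2.279, and 11,000/2.279 = 4827, as stated. Power at 4827 is about 87% (87.2% without the continuity correction). The sample sizes are therefore sound on a two-sided 0.05 test of one pooled effect.

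**2. Set-up.** Let w be the share of statistical information in the reference scheme, and z₁ and z₂ the test statistics within the reference and the other scheme.
- Pooled test: z_p = √w·z₁ + √(1−w)·z₂
- Interaction test: z_i = √(1−w)·z₁ − √w·z₂

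z_p and z_i are independent, while z₁ and z_i have correlation √(1−w). If |z_i| ≤ 1.96, the pooled effect is tested. Otherwise some other contrast is tested.

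The interaction level of 0.05 is taken from section 2. The share w is an **assumption**, because the SAP does not say how much enrolment fell under each scheme. Information per patient is proportional to 1/4 under 1:1 and 2/9 under 2:1, so half the patients under each scheme puts 0.25/(0.25 + 0.222) = 53% of the information in the 1:1 scheme.

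**3. Type I error per endpoint, reading the reference-scheme coefficient.** With no effect in either scheme, the interaction is kept in 5% of trials. Overall error = 0.95 × 0.05 + 0.05 × (rejection rate when kept). The rejection rates come from 4 million simulated pairs (z₁, z₂):

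| w | Rejection rate when kept | Overall type I error |
|---|---|---|
| 10% | about 70% | 8.3% |
| 30% | 49% | 7.2% |
| 50% | 34% | 6.4% |
| 70% | 21% | 5.8% |
| 90% | 10% | 5.3% |

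For example, at w = 50%: 0.0475 + 0.05 × 0.338 = 0.0644.

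**4. Other ways to fill the gap** (share of patients under 2:1 varied from 10% to 90%):
- success if either scheme is significant: 8.0% to 8.7%
- joint two-degree-of-freedom test: 7.2%
- equal-weight average of the two schemes: 5.0% to 7.1%
- size-weighted average: 5.0%
- ceiling for any choice: 0.0475 + 0.05 = 9.75%

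**5. Power with a true common effect and 87% pooled power.** The interaction is still kept by chance in 5% of trials. In those, the reference-scheme test has power of about 50% to 60% for w from 30% to 70%. Overall, 0.95 × 0.87 + 0.05 × 0.50 = 85.2% and 0.95 × 0.87 + 0.05 × 0.60 = 85.7%, a loss of less than 2 points.

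**6. With the interaction left out in advance,** type I error is 5.0% at every share examined.

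**The case against.** Allocation changed during the trial, so checking whether the effect differs by scheme is reasonable, and the rule is written down in advance. That justifies looking at the interaction. It does not justify letting the test choose the primary contrast.

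Four stronger readings are tempting, and the document does not support them:
- **That type I error necessarily exceeds 5%.** It depends on the contrast tested when the term is kept. A size-weighted average would hold 5%. The defect is that no contrast is named.
- **That the trial would lose its pooled comparison.** Tables 3a and 4a also report unadjusted effects. The propensity-matched analyses in sections 6.1 and 6.2 match within randomization scheme and pool over schemes. Only the primary adjusted model loses its pooled estimate.
- **That power falls to 50% to 60%.** This holds only in the 5% of trials where the interaction is kept by chance.
- **That the footnote bears on testing two co-primary endpoints at 0.05 each.** That is a separate question, and its answer may stand in the protocol, which is not at hand.

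The undefined primary effect survives all of this, because it follows from the SAP text whatever the size of the inflation.

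**Conclusion.** The point holds in this limited form. Section 8.3.1 lets a test on the outcome data decide whether each co-primary coefficient is trial-wide or specific to one scheme, and it leaves the result undefined in the second case. This conflicts with the single adjusted effect in Tables 3a and 4a and with the body text, which treats scheme as a covariate only.

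The numerical consequence is modest: 5.8% to 7.2% type I error per endpoint under the most literal reading of the model, and under 2 points of overall power. These figures rest on a large-sample normal approximation to the GEE and Cox models, an interaction test at 0.05, and an assumed information share. The matter should be fixed, but it does not undermine the design.

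**What to change.** Delete the interaction row and its footnote from section 8.3.1. Keep randomization scheme as a covariate, as sections 3.1 and 3.2 already describe. State that the common intervention effect from this model is the primary result for both endpoints, and that the interaction test and scheme-specific effects are supportive only.

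An acceptable alternative is to keep the interaction in both models without testing it and to prespecify the size-weighted average of the two scheme effects as the primary contrast.

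Either change costs a few lines of wording. Either holds type I error at 5.0% in the calculation above and leaves the stated sample sizes unchanged. Scheme-specific effects would still be reported, so nothing is lost if the effect really does differ between schemes.

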8.3.2 Variables for Propensity Score Model

[figure not shown]
Variable	Variable Type
Randomization scheme	Categorical (2:1 vs. 1:1 scheme)
Age	Continuous
Age >=65 vs. <65	Yes/no
Male gender	Yes/no
Race	Categorical (white vs. nonwhite)
Ethnicity	Categorical (Hispanic vs. non-Hispanic)
Insurance Payors	Categorical (private vs. non-private)
Prior MI	Yes/no
Prior PCI	Yes/no
Prior CABG	Yes/no
Prior stroke/TIA	Yes/no
Prior Heart failure	Yes/no
Dialysis	Yes/no
PAD	Yes/no
Hypertension	Yes/no
Diabetes	Yes/no
Current/recent smoker	Yes/no
Weight	Continuous
Transfer in	Yes/no
STEMI	Yes/no
Home P2Y ₁₂ inhibitor	Yes/no
Home aspirin	Yes/no
Creatinine Clearance	Continuous
Nadir hemoglobin	Continuous
Multivessel disease	Yes/no
Access Site	Categorical (Femoral vs. other)
PCI performed	Categorical (multivessel vs. culprit vs. none)
CABG performed	Yes/no
Drug-eluting stent implanted	Yes/no
In-hospital or prior bleeding	Yes/no
In-hospital MI	Yes/no
In-hospital stroke	Yes/no
Cardiogenic shock (Killip IV on presentation or in-hospital cardiogenic shock)	Yes/no
Heart failure (Killip II/III on presentation or in-hospital heart failure)	Yes/no
Cardiac Arrest	Yes/no
Cardiac Rehab Referral	Yes/no
Health Literacy	Yes/no (score >=10 vs. <10)
Baseline angina frequency	Categorical (100 vs. 70-90 vs. 0-60 points)
Baseline PHQ2>3	Categorical
Baseline EQ5D VAS	Continuous

Statistical Analysis Plan

Married	Yes/no
Employed	Yes/no
Education (college graduate)	Yes/no
Baseline financial hardship	Categorical (1 vs. 2/3 vs. 4/5)
Missed >1 dose of medication in the last month	Yes/no
Site: Total bed size	Continuous
Site: Teaching Status	Yes/no
Site: Government hospital	Yes/no
Site: Member of a Healthcare Network	Yes/no
Site: Surgery Capabilities	Yes/no

[figure not shown]
8.4 Appendix: Figure Shells

Figure 1: Consort Diagram

Statistical Analysis Plan

Figure 2a: Consort Diagram under 1:1 randomization

Statistical Analysis Plan

Figure 2b: Consort Diagram under 2:1 randomization
